4.7 Validity Review

The results of the final validity review meeting will be documented in the final list of important deviations, validity findings and assignment to analysis set(s). Any changes to the statistical analysis prompted by the results of the review of study data will be documented in an amendment and, if applicable, in a supplement to this SAP.

4.8 Subgroup analyses

All efficacy and adverse events analyses are also done by subgroups for the following subgroups:

- Sex
- Race
- Age (<65, 65-74, 75-84, >=85)

- Presence of liver metastases at baseline (yes / no)

The presence of liver metastases is defined as having a liver lesion (target or non-target) at baseline. The respective question of the baseline cancer characteristics page is not used for this subgroup definition.

- Primary cancer (colon / rectal)

5. Analysis Sets

5.1 Assignment of analysis sets

Final decisions regarding the assignment of subjects to analysis sets will be made during the validity review of study data and documented in the final list of important deviations, validity findings and assignment to analysis set(s) (see section 4.7).

Population	Description
Enrolled	All participants who sign the ICF
FAS	All participants who have received at least 1 dose of study intervention will be used for efficacy analysis.
SAF	All participants who have received at least 1 dose of study intervention will be used for safety analysis.
IMS	All patients who have received at least one dose of nivolumab and have at least one ADA sample taken (during the treatment or follow-up observation period) that is appropriate for ADA testing (with reportable result) will be included in the analysis of the immunogenicity of nivolumab, which is defined as the immunogenicity analysis set.
Follow-Up (FUP)	All patients who entered the long-term follow-up and have had at least one data collection during the long-term follow-up will be analyzed in the final analysis after study end.

Abbreviations: ADA = anti-drug antibodies; FAS = full analyses set; ICF = informed consent form; PK = pharmacokinetics; r-PKS = regorafenib PK analysis set; n-PKS = nivolumab PK analysis set; IMS = immunogenicity analysis set

No additional treatment assignments to compensate for potential unevaluable patients (e.g. lack of post baseline tumor scans) beyond the needed number of 70 treated patients is planned. Therefore SAF and FAS will be equal and only FAS will be referenced in the analyses.

6. Statistical Methodology

All variables will be analyzed at least descriptively, which includes summary statistics (N, mean, std. dev. minimum, median, maximum) for continuous variables and frequency tables (N, % per category) for categorical variables.

A confirmatory analyses will be conducted only for the primary endpoint at one-sided type-I error level of 2.5% or two-sided type-I error level of 5% respectively. No further confirmatory analysis is intended, and no further tests are conducted. Confidence intervals will be presented for selected variables.

Covid-19:

All COVID-19 related findings will be presented as a separate listing and in applicable tables (e.g. protocol deviations) as separate finding as well.

6.1 Population characteristics

Baseline values and demographic characteristics are defined in section 8.2.7 of the protocol.

All baseline and demographic values will be summarized by descriptive tables as described above.

Baseline cancer characteristics:

Baseline cancer characteristics will be summarized by a table using appropriate summaries. The lines of previous therapies will be analyzed as continuous variable, as well as categorical variable. The variable “liver metastases at baseline according to scans” which is used for the subgrouping of tables, will be added to this table as well as information about patients who had a liver resection.

Medical history

Data for medical history will be coded using the most recent version of MedDRA. Summary statistics (frequency and percentage) will be provided by system organ class (SOC), high level term (HLT) and preferred term (PT).

Medications

The dictionary used for coding medications is the WHO Drug dictionary. Systemic anti-cancer therapies will be displayed by frequency of subjects for each drug, (prior and during follow-up). Diagnostic and therapeutic procedures will be tabulated by frequency of subjects by procedure (prior, concurrent and during follow-up), other concomitant medications will be presented by frequency of subjects for each drug category.

In addition the prior anti-cancer therapies will be displayed, grouped by:

1. Neoadjuvant/adjuvant setting
2. Advanced/metastatic setting

Disposition of Subjects

Since the study is only conducted in the US, the number of subjects enrolled and included in each of the analysis populations will be tabulated overall and by center only. A summary table will also be presented for the number of subjects enrolled and the number and percentage of subjects in each of the defined populations. The reasons for subjects excluded from each of the subject populations will also be tabulated. The reasons for discontinuation of study treatment will be tabulated.

6.2 Efficacy

Analyses will be based on the FAS population.

6.2.1 Sample size

As of amendment 2, it was decided to stop recruitment at 70 treated patients. With this sample size of 70 patients, when the true underlying ORR is 17% or higher and a baseline response rate of 5% is assumed, a one-sided exact binomial test at a type-I error of at approximately 2.5% would result in a power of 92.6%, with at least 8 responders needed to achieve significance.

The location of the primary tumor is a factor and it is expected that 40%-45% of patients will have the primary tumor on the right side. With 31 patients with right-sided tumors, the probability of observing 4 or more responders (ORR 13%) is approximately 80% when the

true underlying response rate is 17%, and the probability of observing 2 or fewer responders (ORR 6.5%) is approximately 80% when the true ORR is 5%.

With 39 patients with left-sided tumors, the probability of observing 6 or more responders (ORR 15%) is approximately 67% when the true underlying response rate is 17%, and the probability of observing 2 or fewer responders (ORR 5.1%) is approximately 70% when the true ORR is 5%.

For this calculation SAS PROC POWER was used.

6.2.2 Primary Endpoint: Overall response rate (ORR) based on RECIST v1.1

Primary endpoint for efficacy assessment is ORR per RECIST v1.1. Radiological tumor assessments will be done locally by the investigator.. ORR is defined as the percentage of subjects with complete response (CR) or partial response (PR) and will be analyzed after all participants met the criteria for primary completion, which is to have 5 post-baseline scans i.e., to have been followed for 10 months, or to have dropped out of the trial. The data base will then be locked for analysis.

The primary analysis of the primary endpoint will investigate the hypothesis

$H_0: \text{ORR}_{\text{Combination}} \leq 5\%$ versus

$H_1: \text{ORR}_{\text{Combination}} > 5\%$

The hypothesis will be tested by a one-sided exact binomial test, assuming a background response rate for the combination to be at most 5%. The target response rate for the combination treatment will be 17%. Using a one-sided exact binomial test at a type-I error of at most 2.5% at least 8 responders out of the 70 patients are needed to achieve significance.

The result of the exact binomial test will be presented in a table, giving the response rate, the number of responders needed, the number of responders observed, the test-statistic and the p-value. Inferential testing will not be repeated by subgroup, only confidence intervals will be presented for the subgroup analysis.

Further analysis of the primary endpoint includes frequency tables (with the ORR table also including all “Best overall response” categories) as well as corresponding 95% two-sided Clopper-Pearson confidence intervals. RECIST results will be displayed by visit as well. All descriptive analyses (incl. confidence intervals) of the primary endpoint will be repeated by two subgroups:

- primary tumor side (right and left). The information about tumor side does not come from the CRF, but is stored in the IxRS system and has to be transferred to the database. .
- ECOG performance status at baseline (0 vs 1)

Formal testing of ORR will not be done for these subgroups.

6.2.3 Secondary endpoints

Overall survival (OS):

Overall survival is defined as the time (days) from the date of first treatment to the date of death.

OS for subjects who are still alive and in the study or who are lost to follow-up at the point of analysis will be censored at the last available date.

OS for subjects who have no post baseline information will be censored at day 1.

Progression free survival (PFS):

PFS is defined as the time (days) from the date of first treatment to the date of radiological or clinical disease progression or death due to any cause, if death occurs before progression is documented.

PFS for subjects without radiological or clinical tumor progression or death at the time of analysis will be censored at their last date of tumor evaluation.

PFS for subjects who have no tumor assessment post baseline and are still alive will be censored at day 1. Patients that report a PD after missed tumor assessment(s) will be censored at the last scan date the patient was known to be progression free.

Disease control rate (DCR):

Disease control rate is defined as the proportion of patients whose best response was complete response (CR), partial response (PR) or stable disease (SD). DCR will be evaluated at 8, 16, 24, 32 and 40 weeks

Scans collected after first progression disease (PD) will not be considered.

Duration of response (DOR):

Duration of response (for PR and CR) is defined as the time (days) from the first documented objective response of PR or CR, whichever is noted earlier, to disease progression or death (if death occurs before progression is documented). Duration of response will be defined for responders only, i.e. subjects with CR or PR.

Time to response (TTR):

Time to response is defined as the time (days) from first treatment until CR or PR and will be derived for responders only.

Duration of stable disease (DoSD):

[figure not shown]
Duration of stable disease is defined as the time (days) from first treatment to date that disease progression or death (if death occurs before progression) is first documented. This variable will only be calculated for subjects who failed to achieve a best response of CR or PR (i.e. calculated for subjects with SD as best overall response). Also subjects, who have no evaluable tumor assessments post-baseline available, will be excluded. The actual dates that the tumor scans were performed will be used for this calculation. Duration of stable disease for subjects without disease progression or death before progression at the time of analysis will be censored at the date of their last tumor assessment.

For analyses of the secondary endpoints, proportion-based efficacy variables will be using frequency tables as well as 95% two-sided Clopper-Pearson confidence intervals. With regard to time to event data, these will be summarized descriptively using Kaplan-Meier

methodology and plots, as well as median estimates based on Greenwood's formula, including 95% two-sided confidence interval. Kaplan-Meier analysis will be displayed in a table as well, giving the number of patients under risk, the number of events and the number of censoring for time intervals of 3 months duration. Kaplan-Meier Plots will present the number of patients under risk for each time point of the x-axis. Kaplan-Meier Plots and matching tables will be created for the subgroups

- Presence of liver metastases at baseline
- Primary tumor
- Primary side of tumor only.

Continuous endpoints will analyzed using summary statistics tables including 95% two-sided confidence intervals.

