7.2 Lost to Follow-up

A participant will be considered lost to FU if he or she repeatedly fails to return for scheduled visits and is unable to be contacted by the study site.

The following actions must be taken if a participant fails to return to the clinic for a required study visit:

- The site must attempt to contact the participant and reschedule the missed visit as soon as possible and counsel the participant on the importance of maintaining the assigned visit schedule and ascertain whether or not the participant wishes to and/or should continue in the study.
- Before a participant is deemed lost to follow up, the Investigator or designee must make every effort to regain contact with the participant (where possible, 3 telephone calls and, if necessary, a certified letter to the participant's last known mailing address or local equivalent methods). These contact attempts should be documented in the participant's medical record.
- Should the participant continue to be unreachable, he/she will be considered lost to FU.

Discontinuation of specific sites or of the study as a whole are handled as part of Section 10.1.

8. Study Assessments and Procedures

- Study procedures and their timing are summarized in the SoA. Protocol waivers or exemptions are not allowed (pre-specified exceptions requiring discussion with the Sponsor are not considered protocol waivers).
- Immediate safety concerns should be discussed with the Sponsor immediately upon occurrence or awareness to determine if the participant should continue or discontinue study intervention.
- Adherence to the study design requirements, including those specified in the SoA, is essential and required for study conduct.
- All screening evaluations must be completed and reviewed to confirm that potential participants meet all eligibility criteria. The Investigator will maintain a screening log to record details of all participants screened and to confirm eligibility or record reasons for screening failure, as applicable.
- Procedures conducted as part of the participant's routine clinical management (e.g., blood count) and obtained before signing of the ICF may be utilized for screening or baseline purposes provided the procedures met the protocol-specified criteria and were performed within the time frame defined in the SoA.

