9.4.3 Secondary Endpoint(s)

Secondary efficacy endpoints include duration of response (DOR), disease control rate at 8 and 16 weeks, progression free survival (PFS), and overall survival (OS). DOR is defined for responders only as the time from first documentation of response (i.e. CR or PR) until disease progression or death (if death without documented disease progression). Disease control is defined as tumor response of stable disease (SD) or better. PFS is the time from first dose of study medication to disease progression or death, whichever is earlier. For patients who did not progress or die, PFS will be censored at the last evaluable tumor assessment. For patients that started subsequent therapy, PFS will be censored at the start of subsequent therapy. OS is defined as time from first dose to death. For patients who did not die, OS will be censored at the last time point at which the survival status is known to be alive.

For analyses of the secondary endpoints, proportion-based efficacy variables will be using frequency tables as well as 95% two-sided Clopper-Pearson confidence intervals. With regard to time to event data, these will be summarized descriptively using Kaplan Meier methodology and plots, as well as median estimates based on Greenwood's formula, including 95% two-sided confidence interval. Continuous endpoints will be analyzed using summary statistics tables including 95% two-sided confidence intervals.

For the analysis of PFS and OS, PFS and OS rates at specific time points such as 6, 12, and 18 months will also be provided based on the Kaplan-Meier method.

CCI

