4.2 Handling of Dropouts

All patients who discontinue the study after enrollment for any reason except death before the protocol defined end are considered drop-outs. Data of drop-outs will be used up to the point of study discontinuation, however no imputation for missing values will be done, except for dates (see below).

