4.3 Handling of Missing Data

All missing or partial data will be presented in the subject data listing as they are recorded on the Case Report Form (CRF).

The number of subjects who prematurely discontinue the study and study treatment for any reason, as well as the reasons for premature discontinuation of study and study treatment, will be reported.

Missing or unevaluable tumor assessments, including scheduled assessments that were not done and incomplete assessments that did not result in an unambiguous tumor response evaluation according to RECIST 1.1, will not be used in the calculation of derived efficacy variables related to tumor assessments unless a new lesion occurred or the lesions that were evaluated already showed progressive disease. No imputation will be performed for missing lesion assessments and tumor response evaluation.

If a date is incomplete, (e.g. only year and month of date of tumor assessment or date of death is available), then day 15 of the month will be used for the calculation of, for example, overall survival and progression free survival. For imputation of AE dates, if the range of possible dates (e.g. a month, if day is missing) and during this time period “treatment emergent” and “non treatment emergent” is possible, the date will be imputed such that the AE will be “treatment emergent” (e.g. the day of treatment start if day is missing).

If the actual scan date of the radiological progression is missing and radiological or clinical progression has been documented based on criteria specified in the protocol, the scheduled scan date will be used to calculate the time to progression.

Safety variables, medical history and concomitant medications:

Treatment emergent AEs, treatment phases, period and relative days will be derived according to data management programming, the operations manual and standard guidelines.

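### SAP 6.2.3 leaves the OS censoring date undefined, at odds with the protocol's known-alive rule, and SAP 4.3 sets partial death dates to day 15 with no floor

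*SAP*

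**What the plan says.** **OS censoring.** SAP 6.2.3 states: "OS for subjects who are still alive and in the study or who are lost to follow-up at the point of analysis will be censored". The date it gives is in the words "will be censored at the last available date". Patients with no post-baseline information are censored at day 1. SAP 4.2 (dropouts), 4.3 (missing data) and 4.6 (data rules) do not say which records supply the date. Protocol 9.4.3 has a more precise rule for patients who did not die: "OS will be censored at the last time point at which the survival status is known to be alive".

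**Partial dates.** SAP 4.3 deals with incomplete dates, for instance where "only year and month of date of tumor assessment or date of death is available". In that case, "then day 15 of the month will be used for the calculation of, for example, overall survival and progression free survival". No lower bound is given, either at the last date known alive or at first dose. The same paragraph imputes AE dates by context, so that an ambiguous AE counts as treatment-emergent. Death dates have no comparable safeguard.

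**The concern.** The documents are dated a week apart (SAP 11 November 2020, protocol Amendment 2 18 November 2020) and should give one censoring rule for OS. The protocol's rule rests on observed status. So do the SAP's own PFS rules, which censor at the last tumor evaluation or the last scan known to be progression-free. The SAP's OS rule does not say what must have been observed. For a patient lost to follow-up, the latest date on file may be later than the last evidence of life, and using it would credit survival that nobody observed.

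The SAP sentence also names only two groups. A patient who withdrew consent while alive, which Protocol 7.1 provides for, is neither still in the study nor lost to follow-up.

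The day-15 rule is a different matter, because it needs no interpretation. Followed exactly, it can give a survival time that the patient's own records contradict.

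**Working it through.** **1. The plan's own figure.** The documents give no planning figure for OS. The ORR design (n = 70, at least 8 responders, 5% against 17%) reproduces by exact binomial: type I error 2.34%, power 92.6% as stated. It does not use OS dates, so nothing below affects it.

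**2. Size of the day-15 error.** If the true death day is d in a month of L days, the error is 15 − d. It runs from 15 − L to +14, so from −16 (L = 31) to +14 days. If d is uniform (assumption), the mean is 15 − (L + 1)/2:

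- L = 28: +0.5 day
- L = 30: −0.5 day
- L = 31: −1.0 day

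**3. Impossible times (hypothetical patients).**

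- First dose 10 January 2020, known alive 24 August 2020 (227 days later), death recorded as August 2020. Day 15 gives 15 August, or 218 days, which is 9 days before the alive record. With a floor at the day after last known alive, the death falls on 25 August, or 228 days.
- First dose 20 March 2020, death recorded as March 2020. Day 15 gives 15 − 20 = −5 days.

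**4. How often a partially dated death would precede the last alive date.** This happens when d > 15 and the gap from last contact to death is shorter than d − 15. Take a 30-day month, d uniform, and k = d − 15 running from 1 to 15. All gap distributions are assumptions.

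- Exponential gap with mean m: (1/30) Σ (1 − e^(−k/m)). For m = 15, 30 and 45 days this gives 19%, 11% and 8%.
- Gap uniform over a contact interval of g days: (1/30) Σ k/g = 120/(30g) = 4/g. The 3-month interval in Protocol 4.1.4 (g = 91) gives 4.4%. The monthly contact also mentioned in Protocol Appendix 6 (g = 30) gives 13.3%.
- If the last contact is known to lie in the death month, uniform from day 1 to the death day: (1/L) Σ (d − 15)/d over d = 16 to L, which is 14-17% for L = 28 to 31.

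The range is therefore about 4-19% of partially dated deaths, not of all deaths. The documents give no expected number of partial death dates.

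**5. OS censoring under the adverse reading.** These are simulations with n = 70. The median, the loss rate and the lag are all assumptions. Every lost patient is censored one lag after the last date known alive.

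| True median (months) | Lost | Lag (months) | KM median, last known alive | KM median, later date |
|---|---|---|---|---|
| 10 | 10% | 1 | 10.12 | 10.21 |
| 10 | 10% | 3 | 10.07 | 10.32 |
| 10 | 20% | 1 | 10.17 | 10.34 |
| 10 | 20% | 3 | 10.10 | 10.61 |

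A second set (exponential OS, loss uniform over 0-18 months, lag of 3 months, 10%, 20% and 30% lost) gives rises of about 0.1, 0.3 and 0.4 month for a median of 8, and 0.2, 0.4 and 0.7 month for a median of 12. At 10-20% lost, the shift is thus about 0.1-0.5 month. For comparison, the sampling SD of the median with 70 patients and a true median of 10 months is about 1.8-2.0 months (administrative censoring at 10-18 months assumed).

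**The case against.** The strongest reply is that the SAP's censoring date can be read as the last date with survival information, which is the protocol's rule. The next SAP sentence, on patients without post-baseline information, supports that reading. This stands. A reader might infer that the SAP rule necessarily biases OS upward, but the documents do not support that: overstatement needs someone to choose a later, non-contact date.

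A reader might also infer that failed contact attempts would become the censoring date, since Protocol 7.2 asks for "3 telephone calls and, if necessary, a certified letter". That section has the attempts documented in the medical record, and nothing shows them as analysis dates. SAP 4.2 adds: "Data of drop-outs will be used up to the point of study discontinuation". This limits what is used, but for a lost patient the point of discontinuation may itself be later than the last contact. A disposition date therefore remains possible, though nothing shows it is intended.

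Nor can one infer that the SAP deliberately overrides the protocol. The protocol amendment is the later document, and text in SAP section 7, on changes to the planned analysis, is blacked out.

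A third tempting inference is that day 15 would place progression before an earlier scan. That needs an earlier scan after day 15 and a progression scan in the same month, so at most 31 − 16 = 15 days apart. Scheduled first-year scans are at least 56 − 14 = 42 days apart even with both windows used, and later ones are spaced more widely. Confirmatory scans come at least 4 weeks after the first. Protocol 8.1 allows repeat scans at any time, but SAP 4.6 keeps unscheduled visits out of the analysis. The case is nearly empty.

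Finally, data queries may catch illogical dates, and SAP 4.5 defers details of the long-term follow-up analysis to another document. Both are fair, but neither changes the rules now written in 6.2.3 and 4.3.

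**Conclusion.** The point holds as two small defects in stated rules.

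First, SAP 6.2.3 leaves the OS censoring date undefined, does not match Protocol 9.4.3 and omits patients who withdrew consent while alive. Any effect on median OS is conditional on the adverse reading and, under the assumptions above, is well inside sampling error.

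Second, the missing floor in SAP 4.3 is a certain defect of the rule, though probably a rare one in the data. It is mainly a data-integrity problem: the error is bounded and averages close to zero, but individual survival times can contradict the record.

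OS is a secondary endpoint that is described and not tested, so no confirmatory conclusion is at risk. This is worth correcting because the correction is easy and leaves one rule in both documents.

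**What to change.** - **SAP 6.2.3:** censor every patient not known to have died at the last date known alive, as in Protocol 9.4.3. State which records establish that a patient is alive, and cap the date at the data cutoff.
- **SAP 4.3:** impute a partial death date as the later of day 15 and the day after the last known-alive date, and never before first dose.

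The cost is two SAP sentences and a minor programming change. OS may look slightly shorter if a later date would otherwise have been used.

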
9.4.2 Primary Endpoints 9.4.3 Secondary Endpoints
	
Corrected confidence intervals to 95% from 50%. Added to 9.5.3: For patients that started subsequent therapy, PFS will be censored at the start of subsequent therapy.

9.5 Interim Analysis
	
Modified ...after approximately 50% of the 30-40 participants Correction; main data analysis may be conducted by study statistician and does not require an external statistician. Analyses do not require to be pre-specified in SAP. Deleted: ...due to the exploratory nature of this study... In order to avoid bias during the main analysis, the data look will be conducted by a statistician not involved in the study and the analyses to

Protocol Section	Amendment 1 Revisions
	be conducted will be pre specified in an interim SAP.
10.1.3 Informed Consent Process	Deleted non-required details: Only if the participant voluntarily agrees to sign the pharmacogenetics (PGx) research project informed consent form and has done so, optional study procedures can be performed (e.g., sample collection for optional biomarker testing).
10.2 Appendix 2: Clinical Laboratory Tests	Total Calcium assessment of chemistry panel changed to Calcium (total calcium), calcium ionized or adjusted calcium . Total bilirubin and indirect bilirubin changed to: total and direct bilirubin . Deleted assessments not required; RBC Indices, MCV, MCH, %Reticulocytes

In addition to the substantive changes summarized in above table, several changes were made to update administrative details, correct typographical errors, and add clarity; such changes are not itemized in the table.

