6.5.8 Other safety measures

Vital signs (i.e. blood pressure, heart rate, weight and BMI) will be tabulated and summarized by visit for observed values and changes from baseline using descriptive statistics, as appropriate.

Unscheduled vital signs data will be listed (Section 16 of the CSR) only.

7. Document history and changes in the planned statistical analysis

This is the first amendment of the SAP.

CCI

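### SAP 6.2.3 censors a documented progression after a missed scan and omits the protocol's subsequent-therapy censoring, so PFS lacks one agreed set of rules

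*SAP*

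**What the plan says.** SAP 6.2.3 measures PFS from first treatment to radiological or clinical progression or death, then adds: "Patients that report a PD after missed tumor assessment(s) will be censored at the last scan date". The date meant is the last scan on which the patient was progression-free. The optional plural means that a single missed scan suffices. Deaths after a gap are not mentioned and so stay events. No sensitivity analysis is planned.

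Protocol 9.4.3 reads: "PFS is the time from first dose of study medication to disease progression or death, whichever is earlier". It censors at the last evaluable scan only those patients who neither progressed nor died. It continues: "For patients that started subsequent therapy, PFS will be censored at the start of subsequent therapy". Table 12–1 records that Amendment 1 (8 January 2020) brought that sentence in: "Added to 9.5.3: For patients that started subsequent therapy, PFS will be censored at the start of subsequent therapy". The SAP is dated ten months later (11 November 2020), and its section 6.2.3 has no counterpart. Protocol 9.4.3 also plans that "PFS and OS rates at specific time points such as 6, 12, and 18 months will also be provided".

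Duration of stable disease, also in SAP 6.2.3, runs "from first treatment to date that disease progression or death (if death occurs before progression) is first documented", with no missed-scan exception. SAP 4.3 generally leaves out of the derived efficacy variables "Missing or unevaluable tumor assessments, including scheduled assessments that were not done and incomplete assessments"; it does not set aside a progression seen on a later, evaluable scan. SAP section 7 opens with "This is the first amendment of the SAP" and is redacted after that.

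**The concern.** After a missed scan, a patient whose next scan is clear stays at risk, while a patient whose next scan shows progression is removed as of the last clear scan. Censoring therefore depends on the outcome, and Kaplan-Meier is biased even when scans are missed purely at random. The 6-, 12- and 18-month PFS rates are the outputs exposed to this.

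There are also two conflicts of definition. Within the SAP, the same progression in the same patient can be an event for duration of stable disease and a censored time for PFS. Between the documents, a patient who starts new therapy without progression can have a different PFS status. The trigger is loose as well: SAP 4.3 puts scans not done and incomplete scans in one class, and SAP 6.2.3 does not say whether an unevaluable scan counts as missed.

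**Working it through.** **Plan's own figures.** The documents give no PFS assumption and no missed-scan rate, so there is no PFS figure to reproduce. The one design figure, ORR power of 92.6% with at least 8 of 70 responders, does reproduce. The exact binomial probability of 8 or more is 0.9256 at 17% and 0.0234 at 5%. It does not involve PFS.

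**One patient, two endpoints.** Take stable disease at week 8, week 16 missed, progression at week 24. Duration of stable disease has an event at week 24. Protocol PFS has an event at week 24. SAP PFS is censored at week 8.

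**Exact small example (assumed inputs).** Scans fall every 8 weeks (Protocol 8.1), half of progression-free patients progress in each interval, each scan is missed with probability 0.1, and there are no deaths.

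- Share of patients at any clear scan, or at baseline, whose next finding is a progression after a gap: 0.5×0.1 + (0.5×0.1)×0.5/(1−0.05) = 0.0500 + 0.0263 = 0.0763. The SAP censors them at that scan.
- Week 8: at risk 1 − 0.0763 = 0.9237; events 0.5×0.9 = 0.4500.
- Week 16: at risk 0.9237 − 0.4500 − 0.4500×0.0763 = 0.4393; events 0.4500×0.5×0.9 = 0.2025.
- Week 24: at risk 0.4393 − 0.2025 − 0.2250×0.0763 = 0.2197; events 0.2250×0.5×0.9 = 0.1013.
- SAP rule at week 24: (1−0.4500/0.9237)(1−0.2025/0.4393)(1−0.1013/0.2197) = 0.149.
- Progression as event at week 24: 0.125 + 0.125×0.1 + 0.25×0.01 + 0.5×0.001 = 0.1405. The same sum gives 0.5 + 0.5×0.1 = 0.550 at week 8 and 0.25 + 0.25×0.1 + 0.5×0.01 = 0.280 at week 16.

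| Week | Complete scanning | Progression as event | SAP rule |
|---|---|---|---|
| 8 | 0.500 | 0.550 | 0.513 |
| 16 | 0.250 | 0.280 | 0.276 |
| 24 | 0.125 | 0.141 | 0.149 |

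The SAP rule is always above complete scanning. It overtakes progression-as-event only after the second scan. Dating the progression at the first missed scan gives 0.125×0.9 + 0.0125×(1−0.5/0.95) = 0.118 at week 24, just below the complete value.

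**Simulation on the protocol schedule (every 8 weeks to week 48, then every 12).** Assumed central case: median PFS 3 months, 10% of first events are deaths, median survival after progression 7 months, scans missed at random, full follow-up.

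| Scans missed | Progressions censored, of 70 | 6-month PFS: complete | Progression as event | SAP rule | SAP minus complete |
|---|---|---|---|---|---|
| 5% | about 4 | 27.5% | 28.2% | 29.0% | 1.5 |
| 10% | about 8 | 27.5% | 28.8% | 30.4% | 2.9 |
| 15% | about 12 | 27.5% | 29.7% | 31.9% | 4.4 |

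- Across 27 scenarios (median 2–4 months, 0–20% deaths, 5–15% missed), the SAP rule exceeded complete scanning at 6 months by 0.8–7.1 points and progression-as-event by 0.3–4.3 points.
- With scans after progression missed 2–4 times as often (108 scenarios), it stayed above complete scanning throughout. Against progression-as-event, the 6-month order could reverse by 0.1–1.8 points at a 2-month median with 40–60% of post-progression scans missed.
- In the 15% case, also censoring deaths after a gap raised 6-month PFS further, to 32.8%. Keeping deaths as events is therefore not the cause.
- At 3 months in the 10% case the values are 62.9% complete, 63.8% SAP rule and 65.5% progression-as-event.
- At 12 months the central case gives 7.5% complete against 8.4/9.3/10.3% under the SAP rule. This is illustrative only, for the follow-up reason given in the verdict.

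**Subsequent therapy.** Follow-up scans stop when new systemic therapy starts (Protocol 8.1), but survival follow-up continues (Protocol 4.1.4). A patient who switches without progression and later dies is censored at the switch under the protocol. Under SAP 6.2.3 that patient stays at risk and has an event at death. With 10–30% switching without progression (assumed), 5–25% of patients change event status. SAP minus protocol from this omission alone ranged from −2.8 to +5.0 points at 6 months and from −6.3 to +0.2 at 12.

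**Both departures together.** Central case, 10% of scans missed, 20% switching, 7-month median survival after the switch, data cutoff 10–16 months after first dose (all assumed). At 6 months the SAP gives 34.5% and the protocol 31.9%. At 12 months the SAP gives 8.3%, the protocol 8.7% and complete scanning 8.8%. With a 4-month median the 12-month values are 14.9%, 16.0% and 16.2%.

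**The case against.** Protocol 9.4 leaves missing-data procedures to the SAP, so having a missed-scan rule is legitimate, and neither convention is unbiased. Progression-as-event dates the progression late, and at 3 months it is further from complete scanning than the SAP rule. SAP 6.2.3 tabulates Kaplan-Meier results in 3-month intervals, so that early point is on view. This stands, and it is why the fix adds a run with the earlier date. It does not rescue a rule that discards an observed event because of what the next scan shows, while a sister endpoint keeps that event.

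On therapy, SAP 6.2.3 is silent rather than contrary, and the redacted section 7 may state a deviation. A living patient who switched without progression is censored under both documents; status differs mainly for deaths after a switch. All of that stands, so this half of the point is conditional.

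The effect is modest, on an untested endpoint, and every rate above is assumed. That also stands.

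A reader might infer that the SAP as a whole overstates PFS at 6, 12 and 18 months relative to the protocol. The documents do not support this. The upward direction belongs to the missed-scan rule taken alone, and in the combined runs the 12-month rate is lower under the SAP.

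**Conclusion.** The point holds in this form. SAP 6.2.3 turns a documented progression after one or more missed scans into a censored time, in conflict with Protocol 9.4.3 and with the SAP's duration of stable disease. Taken alone, the rule raises PFS rates from 6 months onward relative to complete scanning, by about 1.5 to 4.4 points at 6 months in the central assumed case. SAP 6.2.3 also omits the protocol's subsequent-therapy censoring, unless section 7 accounts for it. The net SAP-minus-protocol difference is not determined.

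The 12- and 18-month sizes should not be relied on or set against a standard error computed for 70 fully followed patients. Primary completion (Protocol 4.4, SAP 6.2.2) comes at about 10 months of follow-up for the last patients. The later long-term analysis in SAP 4.5 lists overall survival, not PFS. How many patients would be at risk at 12 or 18 months is unknown.

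PFS is a descriptive secondary endpoint. The primary ORR test is unaffected.

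**What to change.** 1. In the main PFS analysis, count a progression found after missed scans as an event at its documented date, as Protocol 9.4.3 and duration of stable disease already do.
2. Report the present SAP censoring as a sensitivity analysis, and state there whether an unevaluable scan under SAP 4.3 counts as missed.
3. Add one run that dates such a progression at the first missed scheduled scan. For a patient with a documented progression, this date and the documented date bracket the scheduled scan that would have found it. The run also shows how favourable late dating is, especially at 3 months.
4. Carry the protocol's subsequent-therapy censoring into SAP 6.2.3, with a sensitivity analysis that ignores new therapy. If section 7 already states a deviation, refer to it from 6.2.3.

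The cost is SAP wording and three extra runs on data already collected. The reported 6-month PFS may look slightly less favourable.
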